**Version Date: 12/07/2021**

**I. BACKGROUND AND SIGNIFICANCE**

**a. Historical Background**

**It is critical to treat depression in patients with acute coronary syndrome (ACS).** Among the one million ACS patients in the U.S. each year (e.g., myocardial infarction, unstable angina), up to 45% have elevated depression symptoms. Even mild elevations in depression symptoms double the risk of mortality after ACS. Meta-analyses of over 4,000 ACS patients and 53 studies have found that depression is an independent risk factor for recurrent cardiac events, re-hospitalizations, cardiac mortality, and all-cause mortality, beyond other traditional risk factors. Left untreated, depression persists for years and doubles the risk of death through biological and behavioral mechanisms. Biologically, depression causes inflammation through neuroendocrine alterations, leading to atherosclerotic plaque formation and rupture. Behaviorally, ACS patients need to make multiple lifestyle changes, but depression symptoms (e.g., disinterest, lack of motivation) prevent engagement in cardiac health behaviors (e.g., physical activity, diet). Thus, depression treatment is necessary to promote biological and behavioral changes important for survival.

**Depression treatments for ACS patients need improvement.** More ACS patients prefer psychological (75%) rather than pharmacological depression treatments (20%). However, the recommended psychological intervention, cognitive-behavioral therapy (CBT), has limited effects on depression and cardiac outcomes. Targeting the mechanisms that link depression to ACS could improve treatment efficacy, but CBT does not aim to target a key mechanism, i.e., inflammation. Consistent evidence from multiple meta-analyses suggests that depression is associated with elevated levels of inflammatory cytokines, particularly C-reactive protein (CRP), interleukin-6 (IL-6), and TNF- $\alpha$ . These same specific cytokines are also elevated, positively correlated with depression symptoms, and independently increase the risk of mortality in patients with cardiac disease. Of note for depression treatment, the relationships are bidirectional: treating depression reduces inflammation, but reducing inflammation also reduces depression symptoms, making CRP, IL-6, and TNF- $\alpha$  salient treatment targets for both depression and cardiac health in ACS patients.

**Mindfulness-Based Cognitive Therapy (MBCT) could improve depression and cardiac health for ACS patients.** MBCT is an 8-week manualized group intervention that combines CBT with mindfulness meditation to treat depression; it is as effective as antidepressant medication for relapse prevention and reduces symptoms in active depression. The American Heart Association (AHA) recently highlighted the potential benefits of meditation for cardiac health and the need for

further research in this area. Indeed, through the addition of mindfulness training, MBCT could improve both depression and cardiac health. First, mindfulness meditation can reduce levels of CRP, IL-6, and TNF- $\alpha$ , which reduces depression symptoms and benefits cardiac health. Second, meditation increases pro-sociality (e.g., compassion, altruism) and social support, both of which reduce depression symptoms. Given that social isolation is an independent risk factor for ACS mortality and pro-sociality improves cardiovascular functioning, social improvements could have direct benefits on cardiac health. Next, MBCT improves emotion regulation (e.g., rumination about a recurrent event, acceptance of lifestyle changes), which is a key treatment target for depression. Lastly, mindfulness training improves cardiac health behaviors, likely by improving emotional outcomes. Improvements in depression also lead to further improvements in inflammation and pro-sociality to further promote cardiac health.

**b. Previous pre-clinical or clinical studies leading up to and supporting the proposed research**

**Research supports the feasibility of MBCT for depression treatment in ACS patients.** Two meta-analyses (18 trials) have demonstrated that mindfulness interventions are feasible, acceptable, and reduce depression symptoms in patients with cardiovascular disease ( $d = .35 - .61$ ). ACS patients are similar to other cardiac disease patients (e.g., age, comorbidities) and thus are also likely to find mindfulness interventions acceptable. In fact, ACS patients may be most interested in depression treatment because they are motivated to improve their health following the acute cardiac event. Most research in patients with cardiovascular disease has used Mindfulness-Based Stress Reduction (MBSR), which is very similar to MBCT, but does not incorporate a CBT approach to target depression specifically. MBCT shows larger effect sizes for depression than MBSR and thus might be particularly useful for ACS depression treatment.

**An electronic health (e-health) approach is needed to improve treatment outreach.** Most ACS patients prefer behavioral depression treatments, but these are burdensome, not widely accessible, and present barriers. In a study of nearly 700 primary care patients, 78% of those with depression reported logistical and emotional/physical barriers to accessing treatment. E-health technologies can overcome these barriers to reach more patients and effectively treat depression. In a study of over 200 patients with cardiovascular disease, 85% had internet access and 74% of them preferred e-health interventions. ACS patients tend to be older adults ( $\geq 65$  years), the fastest growing group of computer and internet users, who report positive experiences with technology used at home. A systematic review of 54 trials found that e-health interventions are feasible for older adults with medical problems, including those with cardiovascular disease.

**It is feasible to deliver MBCT via e-health technologies.** E-health mindfulness interventions are feasible and can improve health outcomes in patients with medical problems. However, research has focused on websites that patients use independently, which does not allow for synchronous contact with a clinician or peers, leading to a smaller treatment effect and increased attrition, and eliminating the health benefits of social support. Group videoconferencing combines accessibility with synchronous contact, shows comparable efficacy with in-person treatments, and is a validated approach to behavioral intervention delivery. Two studies demonstrated the feasibility of videoconferencing to deliver mindfulness interventions to patients at their own home. Thus, group videoconferencing is a promising but underutilized approach to MBCT delivery.

**MBCT via group videoconferencing is likely to be attractive and feasible for ACS patients.** Web-based mindfulness interventions are feasible and reduce depression symptoms in patients with cardiovascular disease and other older adult populations. The AHA has emphasized that a benefit of meditation for cardiac health is the possibility of online delivery, but no research has applied MBCT via group videoconferencing to ACS patients with elevated depression symptoms.

**Our preliminary work supports the use of virtual MBCT for ACS patients.** We recently conducted a qualitative study (individual patient interviews) to solicit patient's perspectives and needs for a behavioral depression treatment based on MBCT (IRB Protocol Number 2018P001000). Patients were open and interested in a mindfulness program, identified a range of symptoms and needs for the intervention to target, offered suggestions for promoting videoconferencing feasibility, and expressed openness to participate in dried blood spot research procedures. We developed an adapted MBCT protocol based on this feedback, which we recently tested in an open pilot trial of n=7 patients with ACS and depressive symptoms (IRB Protocol Number 2020P000045). Those who completed the intervention (n=4) reported high ratings of intervention acceptability, videoconference acceptability, comfort with the dried blood spot procedures, and improvements in depression and anxiety symptoms.

**c. Rationale behind the proposed research and potential benefits to patients and/or society**

The rationale behind the proposed research is that the high comorbidity between depression and cardiovascular disease reflects a complex, mind-body interaction that must be treated using a comprehensive mind-body approach. Mindfulness-based cognitive therapy is an evidence-based intervention with efficacy to treat depression, and improve quality of life in patients with cardiovascular disease. However, this is the first research to adapt MBCT specifically to the needs of patients with depression after an acute cardiac event, test the efficacy of this intervention an randomized trial with an active control group. The potential

benefits to patients in the trial include peer support, attention from a trained clinician, and learning information and skills to improve mood, coping, cardiac health, and quality of life. Given that cardiovascular disease is the leading cause of death worldwide, and the substantial added burden of co-occurring depression and cardiovascular disease, the proposed research has the potential to identify a novel, efficacious, and scalable intervention to improve public health.

## II. SPECIFIC AIMS

- a. Aim 1:** To establish, in a pilot RCT (approx. N=50 participants) with a time- and attention-matched health enhancement control, (a) the feasibility of the recruitment procedures (screening, eligibility, enrollment rates), and feasibility and acceptability of the (b) MBCT and control interventions (adherence, retention, fidelity, satisfaction, group videoconferencing delivery) and (c) data collection procedures by group (adherence, satisfaction). Hypothesis 1a: Recruitment will be feasible as evidenced by screening, eligibility, and enrollment rates; (1b) the MBCT and control interventions and (1c) data collection procedures in both groups will be feasible and acceptable.
- b. Aim 2 (exploratory):** To explore within-group changes in psychosocial and physical health outcomes following virtual MBCT and the control intervention (e.g., depression, inflammation, emotion regulation, pro-sociality, and health behaviors).

## III. SUBJECT SELECTION

### a. Inclusion/exclusion criteria

#### **Inclusion criteria:**

1. Lifetime ACS per medical record and/or patient confirmation
2. Current elevated depression symptoms (PHQ-9 $\geq$ 5)
3. Age 35-85 years
4. Access to high-speed internet
5. Massachusetts General Brigham patient

#### **Exclusion criteria:**

1. Active suicidal ideation or past-year psychiatric hospitalization (per patient report and/or medical record review)
2. Non-English-speaking
3. Cognitive impairments preventing informed consent per medical record review and/or cognitive Screen  $\leq$ 4
4. Patient deemed unable to complete the study protocol or has a condition that would likely interfere with the study
5. Is not a Massachusetts General Brigham patient

## **b. Source of subjects and recruitment methods**

Study staff will engage in multiple recruitment modalities to obtain a diverse sample of study participants.

First, patients will be recruited through the RPDR. We will include patients who have and have not agreed to participate in RODY (Research Options Direct to You).

“RODY No” patients identified from the RPDR will be sent a combined opt-out letter from a member of their healthcare team (e.g., cardiologist, primary care provider, nurse practitioner, etc.) and the study team. This letter will be sent via paper mail or Patient Gateway. This letter will describe the study procedures and ask patients to contact the study team within 2 weeks if they would not like to be contacted to hear more about the study. Patients will have the option to opt-out via phone or email. Those who do not opt-out will be contacted via phone by the PI or a trained and CITI-certified research staff member. Patients will be read a brief phone script (attached) informing them of the purpose of the call and asking if they would like to hear more about the research study. Those who agree will undergo eligibility screening (attached). Those who are eligible and interested will undergo informed consent, described below.

“RODY Yes” patients will receive an opt-out letter from the study team (attached). All other recruitment procedures will be the same as for “RODY No”.

Only the Principal Investigator and trained research staff will identify and contact patients. Up to approximately 3 calls will be made to a given patient before assuming the patient is not interested and no longer attempting to contact them.

Second, patients will be recruited through hospital flyers (e.g., inpatient/outpatient cardiology clinics, psychiatry clinics). Advertisements will ask patients to contact study staff if they are interested in learning more about the study. In situations where a briefer ad is more feasible (e.g. virtual postings on iPads and computer screens in clinic waiting rooms), a shortened version of the flyer will be posted. The flyers are included in the IRB submission. Specific phone numbers on the flyers will be filled in based on the contact information for the current RA. Phone screening and consenting procedures will be the same as described above.

Third, patients will be recruited via direct referrals from their providers (e.g., cardiologists, psychiatrists). We will inform providers about the study (e.g., via short presentations at their team meetings) and provide them with flyers. Providers may either obtain verbal permission from the patient to share their name and contact information with study staff, or they may provide patients with the flyer to contact study staff on their own. The outreach and phone screening procedures will be the same as described above.

Fourth, patients will be recruited from inpatient cardiac units within MGH. Study staff will review inpatient censuses from MGH cardiac units and/or participate with invitation in inpatient cardiology rounds to identify patients whose available admission information (e.g., laboratory studies) suggests ACS. Study staff will ask the clinical team to confirm the cardiac diagnosis and inquire with the patient whether the patient is willing to hear about an optional study. For willing patients, study staff will discuss the study with the patient and assess for additional study criteria using the same screening procedures described above (e.g., PHQ-9 administration). For patients who screen out or decline assessments, we will retain no personal information. Patients who are interested in hearing about the study and completing the screener, but do not want to do so during their hospitalization, will be given the option to be contacted by phone after their discharge. The same screening procedures would be done by phone at that time.

Fifth, research staff will use EPIC to assist in recruitment. To this end, we have worked with the Partners eCare Research Core (PeRC) to set up the necessary steps. PeRC leverages the Epic EHR to assist researchers in identifying and recruiting patients for their research studies conducted at Partners HealthCare. PeRC will put together a report through EPIC based on a list of predetermined variables (please see attached list of variables to be extracted). After Epic training, and hands-on guidance from the PeRC team, study staff will run this automated report within Epic to identify potentially eligible ACS patients. Study staff will review patients' charts to confirm potential eligibility as needed (e.g., confirm admission diagnoses). Study staff will send patients the same opt-out letters described above via paper mail or Patient Gateway according to RODY status, and the outreach and screening procedures will be the same.

In addition, the PI or trained RA will view Epic patient lists for cardiac units (e.g., Ellison 10, Ellison 11) to identify patients admitted for ACS. Patients' charts will be reviewed to determine if they are RODY or non-RODY patients. RODY patients will receive a phone call or opt-out letter inviting them to participate in the study. For non-RODY patients, study staff will obtain permission from a member of the patient's healthcare team to send a combined opt-out letter from the provider and study team.

Sixth, patients will be recruited through the study's MGB Rally page. Research staff will publish an informational Rally page to advertise the study to MGB patients. Patients will be able to contact study staff if they are interested in learning more about the study. Specific phone numbers on the Rally page will be filled in based on the contact information for the current RA. Phone screening and consenting procedures will be the same as described above.

#### **IV. SUBJECT ENROLLMENT**

**a. Methods of enrollment, including procedures for patient registration and or randomization**

Study staff will approach patients about participating in the study using one the modalities discussed in section III.b. For patients who are not interested in participation, study staff will discontinue contact. For patients who are interested in participation, study staff will screen patients for eligibility (criteria detailed in section III.a). If a patient screens as eligible, they will be asked to provide informed consent using one of the procedures detailed in section IV.b. Following informed consent patients will be 1:1 randomized (see section IV.c) and enrolled in the study using a random number generator.

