**c. Treatment assignment and randomization**

Participants will be randomized to a MBCT or a time- and attention-matched health enhancement control in a 1:1 design using a random number generator.

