#### *Survey measures*

The self-report survey measures will be the same for the MBCT and control groups. The surveys will be administered within approximately 1-2 weeks before and after the intervention and at 3 months post-intervention. This battery will include the following validated self-report surveys: Assessment of Survivor Concerns (fear of recurrence), CAMS-R (mindfulness), Cardiac History and Symptoms, Current Experiences Scale (CES; resiliency), COVID items,

demographic questionnaire, Expectancy Questionnaire, Experiences Questionnaire (decentering), Group cohesion scale, Hospital Anxiety and Depression Scale (HADS; depression and anxiety), Interpersonal Reactivity Index (IRI; empathy), MAIA-2 body subscales (interoception), MBCT-AS Checklist (fidelity checklist), PHQ-9 (depression), Medical Outcomes Study – Specific Adherence Scale (MOS-SAS; health behaviors), one item from the Short Form-12 (SF-12), Self-Other Four Immeasurables (SOFI; self and other compassion), PROMIS Physical Function (PROMIS-PF; physical function), and The Positive and Negative Affect Schedule-Positive Affect (PANAS-PA). The post-intervention survey will also include a group cohesiveness measures to assess perceived connection with other group members as well as intervention satisfaction questions to assess acceptability. The 3-month follow-up survey will include questions about continued mindfulness practice. The baseline survey, post-intervention survey and post-intervention survey will all include questions related to COVID-19. All three survey batteries are included in the IRB submission.

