#### *Dried blood spots*

Both intervention and control group participants will be asked to provide dried blood spot samples. Within one week before and after the intervention and 3-months-post intervention, participants will be asked to provide self-collected whole dried blood spots to assess IL-6, CRP, and TNF- $\alpha$ .

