**d. Procedures/surgical interventions**

At baseline, post-intervention, and 3 months following the end of the intervention, participants will be asked to complete a dried blood spot sample collection using a minimally invasive finger skin prick technique, which involves pricking the finger with a lancet, milking the finger to produce 5-10 drops of blood onto filter paper, allowing the blood spots to dry, and mailing it to the study team at MGH in a secure envelope. Prior to the start of the intervention, an RA will guide the participant in self-collecting blood samples via a videoconference call or phone call (per the participant's preference). Participants will also be sent written instructional handouts. The RA will ask the participant a series of questions to gauge understanding, provide corrective feedback, and answer any questions the participant might have before proceeding to guide the participant in the procedure.

Participants will be asked to allow the sample to dry overnight, document the date the sample was taken on the filter paper, and mail it to the study team at MGH the next morning. Samples will be received by the RA, who will mark the date of receipt in the study database. Samples can be in ambient air for up to 2 weeks without degradation. We will ask participants to mail the samples within 24 hours of taking them to minimize the time samples are in ambient air. If samples are received beyond 2 weeks of the date indicated on the filter paper, we will ask participants to provide another sample, and participants will be made aware of this possibility in the consent form. Once received, the RA will bring the samples to be stored in a -20°C freezer in the MGH Clinical Research Center lab or mail them to our collaborator at the Laboratory for Human Biology Research at Northwestern University for storage and processing. Blood spots can be frozen at this temperature for several years without degradation.

When initially mailing the blood spot kit to participants, the RA will indicate the participant's study ID number, group assignment, date, and data collection timepoint on the filter paper. Participants will be informed not to write any personally identifying information on the filter paper. This will keep the blood samples de-identified.

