## **IX. MONITORING AND QUALITY ASSURANCE**

**a. Independent monitoring of source data**

Source materials will include information collected from survey questionnaires at baseline, post-intervention, and 3-month follow-up; exit interviews; weekly practice logs; post-session surveys; and blood spot collection procedures. All self-

report questionnaires will be entered electronically via REDCap. Individual exit interviews will be conducted by phone or videoconferencing. Upon their receipt, all dried blood spot samples will be stored securely in an MGH affiliated lab, on the MGH campus. Samples will later be shipped, in accordance with MGB and CDC guidelines, to our collaborators [name] and [name] at Northwestern University for storage and/or processing. All samples will be labeled with the patient ID, date of collection, group assignment, and time point (baseline, post-intervention, 3-month follow-up). We will follow all CDC shipping guidelines (e.g., placing a freeze pack inside of an insulated shipping container, placing sealed plastic bags containing the samples into a box). We will seal the box tightly with tape and ship specimens via courier to [name] in Health Lab at the Northwestern University Feinberg School of Medicine.

[name] will securely store the samples in his locked lab at Northwestern before bringing them for processing to his collaborator [name] at the Laboratory for Human Biology Research at Northwestern University. The blood samples will not contain identifiers that could be used by the outside collaborators to link the data to individual subjects; they will be labeled with participants' study ID numbers and not any personally-identifying information, and only Partner's study staff will have access to the data file linking participant's personal information to their study ID number. Study staff have completed CDC and HealthStream trainings on dried blood spot storage and shipping and have acquired the proper documentation to ship samples to a non-MGB lab.

All information collected will be for the purposes of research and will only be accessible to study staff and stored securely on the Partners' network. Survey and practice log data will be reviewed for completeness though participants will be allowed to skip any questions they are not comfortable answering.

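### Baseline blood is collected after allocation on a card marked with the arm, the assays are run with the arm visible, and the baseline survey appears to follow randomisation too

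*Combined protocol and SAP*

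**What the plan says.** Section IV.a runs from screening to consent to allocation: "Following informed consent patients will be 1:1 randomized (see section IV.c) and enrolled in the study using a random number generator". Randomisation and enrolment are one step, and neither IV.a nor IV.c requires any baseline measure to be complete first.

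On the blood spots, section V.d says: "When initially mailing the blood spot kit to participants, the RA will indicate the participant's study ID number, group assignment, date, and data collection timepoint", all of this on the filter paper. Section IX.a repeats the labelling for samples at every time point, baseline included, before shipment to the outside collaborators: "All samples will be labeled with the patient ID, date of collection, group assignment, and time point".

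On the questionnaires, section V.a (Survey measures) says: "The surveys will be administered within approximately 1-2 weeks before and after the intervention and at 3 months post-intervention". This ties the survey to the start of the groups and not to randomisation. Section VII.d, describing safety monitoring, gives the baseline PHQ-9 to enrolled participants.

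Section VI.c uses baseline as the first time level in every Aim 2 model, defines change as post-intervention minus baseline, and under Aim 1 compares adherent with non-adherent participants of each group on baseline depression.

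**The concern.** A baseline should be fixed before anyone can react to the allocation. Here the arm exists, and is written on the card, before the baseline sample is drawn. Three things follow.

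- **Self-report.** If participants know their arm when they complete the PHQ-9, HADS and expectancy items, pleasure or disappointment can move those scores, and the shift passes into the change from baseline.
- **Blood.** Participants may decline any blood collection (section VII.a), so knowing the arm could influence who gives a baseline sample. The research assistant who guides collection and the laboratory that runs IL-6, CRP and TNF-α both see the arm, at all three time points.
- **Flow of participants.** Anyone lost between allocation and baseline is a post-randomisation loss without the study baseline. Retention is a primary outcome with a 75% benchmark for post-intervention assessments, and Table 1 does not state its denominator. Where early losses fall therefore affects whether the benchmark is met.

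**Working it through.** The plan has no figure to reproduce: section VI.d reports no power analysis, and no SD, planned dropout or assumed effect is given. The check is mainly one of sequence.

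**Order for blood**

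1. Screening, including a PHQ-9, precedes consent (sections III.b, IV.a, VII.d).
2. Consent is followed by randomisation with enrolment (IV.a). Section IV.c adds only "in a 1:1 design using a random number generator".
3. The kit is mailed with the arm on the card (V.d).
4. The baseline sample is then collected: "Prior to the start of the intervention, an RA will guide the participant in self-collecting blood samples" (V.d). The window in V.a (Dried blood spots) is "Within one week before and after the intervention and 3-months-post intervention".
5. Samples go to the laboratory with the arm on the label (IX.a).

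Step 3 needs a known arm and must precede step 4. So allocation precedes baseline blood, whatever the order of the survey.

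**Order for the survey**

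VII.d gives the baseline PHQ-9 to enrolled participants, and IV.a makes enrolment the same step as randomisation. Together they put the survey after allocation. But IV.a gives no interval after consent. Consent, survey about two weeks before the groups, randomisation, kit, then blood in the last week would also fit the V.a windows. The survey order is therefore probable, not stated.

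**Effect on change**

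Let B and P be the baseline and post-intervention scores, and δ a reaction to allocation that is present at baseline and gone by post-intervention. Observed change = P − (B + δ) = (P − B) − δ. The whole of δ enters the within-arm change with its sign reversed. If δ were 0.1 to 0.2 SD (an assumption; the documents give no value), the change would be off by 0.1 to 0.2 SD.

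**Effect of early losses**

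Assume 5% to 20% are lost between allocation and baseline (again not in the documents). With N=40 (VI.d) that is 0.05 × 40 = 2 to 0.20 × 40 = 8 people. With about 50 (Aim 1) it is 2.5 to 10.

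For scale, Table 1's 75% benchmark for baseline blood, taken over all randomised, needs 30 of 40 (10 may be missing) or 38 of 50 (12 may be missing).

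Now take the 75% post-assessment benchmark with 20 per arm. Over all randomised it needs 0.75 × 20 = 15 completers.

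| Lost early per arm | Remaining | Needed if denominator is those remaining | Needed if denominator is all randomised |
|---|---|---|---|
| 2 | 18 | 14 (70% of randomised) | 15 (83% of remaining) |
| 4 | 16 | 12 (60% of randomised) | 15 (94% of remaining) |

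The chance of meeting 75% over all randomised, both arms together, is P(X ≥ 30) with X ~ Binomial(40, p), or P(X ≥ 38) with X ~ Binomial(50, p). Here p = (1 − early loss) × 0.85, where 85% completion among those remaining is assumed.

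| Early loss | p | N=40 | N=50 |
|---|---|---|---|
| 0% | 0.85 | 0.97 | 0.97 |
| 5% | 0.81 | 0.87 | 0.85 |
| 10% | 0.765 | 0.67 | 0.61 |
| 20% | 0.68 | 0.22 | 0.14 |

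At N=40 and 10% early loss, changing the 85% to 80% or 90% gives 0.41 or 0.88. These figures show sensitivity and do not predict this trial. Identical patient behaviour can look like success or failure depending on which side of randomisation the early losses fall.

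**The case against.** The best case for the plan has several parts.

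- **Survey order is not stated.** A reader might infer that participants are randomised immediately after consent and complete the PHQ-9 and HADS knowing their arm. The text says neither, and Figure 1, which outlines data collection, is not available here. This objection stands: for the survey the point is an inference.
- **The direct evidence and the main mechanism differ.** The marked card concerns blood, whereas a reaction to allocation concerns mood and expectancy. The card might also carry a code and not the name of the program, although none is described. This stands in part. It does not touch the fact that blood is collected after allocation, or the visibility of the arm to staff and laboratory.
- **No arm comparison is planned.** A reader might infer that early losses spoil a comparison of adherence or retention between MBCT and control. Section VI.c contains no such test; Aim 1 is descriptive against benchmarks and Aim 2 is within-group and exploratory. This stands.
- **Early losses are not wholly without data.** They have a screening PHQ-9 and may have health-record data. That is correct, though the screening score serves eligibility and is not named as the analysis baseline.
- **The size is unknown.** It is tempting to set 0.1 to 0.2 SD against the d of .35 to .61 in section I.b and call the bias 16% (0.1/0.61) to 57% (0.2/0.35) of the effect. The shift is assumed, the range pairs opposite extremes, and I.b does not say whether those d values are within or between groups. The documents do not support that scaling.
- **Losses after allocation are themselves feasibility information.** Moving randomisation later could hide them. This is a fair warning, and the change must guard against it.

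**Conclusion.** The point holds in a limited form. For blood it rests on the text alone: the baseline sample follows allocation, on a card that shows the arm, and the arm stays on the label through assay. That the participant sees it is likely but not stated. For the survey, collection after randomisation is the more natural reading of sections IV.a and VII.d together, with moderate confidence.

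The consequences are confined to the exploratory Aim 2 changes, the adherent versus non-adherent comparison on baseline depression, and the counting of early losses against benchmarks. The documents do not allow the size of any of these to be derived; every shift, loss and retention rate in the tables and ranges above is an assumption. The primary outcomes are feasibility and acceptability, so this does not threaten the trial's main purpose. It is worth correcting because the remedy costs little and because section VIII.b says the pilot is to inform a later efficacy trial, where the same sequence would affect a between-arm comparison.

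**What to change.** 1. In sections V.d and IX.a, label cards with study ID, date and timepoint only, and hold the arm in the study database. The ID already links the sample, so nothing is lost.
2. In IV.a and IV.c, state that randomisation, or at least disclosure of the arm, takes place only after the baseline survey is complete and the baseline blood sample has been collected or declined. Receipt of the sample need not be awaited. Adjust the one-week blood window in V.a and V.e if the steps do not fit inside it.
3. If expectancy about the assigned program is wanted, give that questionnaire alone after disclosure.
4. Report losses between consent and randomisation as their own line in the recruitment flow, and define retention in Table 1 over all randomised, so that later randomisation does not flatter the benchmark.

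The cost is protocol wording and a reordering of staff steps, with no new assessment. The drawbacks are later disclosure of the arm, tighter scheduling before the groups start, and slightly fewer people randomised than consented. If staff already collect the survey before allocation, item 2 reduces for the survey to one clarifying sentence; item 1 is needed either way.
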